3.1.13 Negative pregnancy test for females of childbearing potential only

3.2 Exclusion Criteria

3.1.14 Extramedullary relapse involving immuno-privileged sites (e.g. CNS, testes, eyes). Other sites of extramedullary relapse (e.g. leukemia cutis, granulocytic sarcoma) are acceptable.

3.1.15 Participants who had cytotoxic chemotherapy or other investigational agents within 4 weeks prior to cell infusion (6 weeks for nitrosoureas or mitomycin C), or immunotherapy within 8 weeks prior, or those who have not recovered from adverse events due to agents administered more than 4 weeks prior. Use of hydroxyurea, HMAS (e.g. azacytidine, decitabine) and/or approved novel agents (e.g. venetoclax, FLT3 inhibitors, IDH1/2 inhibitors etc.) to control counts within 4 weeks prior to cell infusion is permitted.

3.1.16 Prior history of DLI

3.1.17 Prior history of treatment with anti-CTLA-4 or anti-PD-1 pathway therapy, or CD137 agonist therapy.

3.1.18 Prior history of severe (grade 3 or 4) acute GVHD, or ongoing active GVHD requiring systemic treatment.

3.1.19 Organ transplant (allograft) recipient.

3.1.20 History of allergic reactions attributed to compounds of similar chemical or biologic composition to Ipilimumab or other agents used in study.

CONFIDENTIAL

This document is confidential. Do not disclose or use except as authorized.

- 3.1.21** Autoimmune disease: Patients with a history of inflammatory bowel disease, including ulcerative colitis and Crohn's Disease, are excluded from this study, as are patients with a history of symptomatic disease (e.g., rheumatoid arthritis, systemic progressive sclerosis [scleroderma], systemic lupus erythematosus, autoimmune vasculitis [e.g., Wegener's Granulomatosis]) and motor neuropathy considered of autoimmune origin (e.g. Guillain-Barre Syndrome and Myasthenia Gravis). Patients with Hashimoto's thyroiditis are eligible to go on study.
- 3.1.22** Uncontrolled intercurrent illness including, but not limited to, ongoing or active infection, symptomatic congestive heart failure, unstable angina pectoris, cardiac arrhythmia, or psychiatric illness/social situations that would limit compliance with study requirements.
- 3.1.23** Pregnant women are excluded from this study because of the unknown teratogenic risk. Because there is an unknown but potential risk for adverse events in nursing infants secondary to treatment of the mother, breastfeeding should be discontinued if the mother is treated on this study.
- 3.1.24** HIV-positive participants on combination antiretroviral therapy are ineligible because of the potential for pharmacokinetic interactions with *agents used in this study*. In addition, these participants are at increased risk of lethal infections when treated with marrow-suppressive therapy. Appropriate studies will be undertaken in participants receiving combination antiretroviral therapy when indicated.
- 3.1.25** Individuals with active uncontrolled hepatitis B or C are ineligible as they are at high risk of lethal treatment-related hepatotoxicity after HCT.

3.3 Inclusion of Women and Minorities

Both men and women of all races and ethnic groups are eligible for this trial.

4. REGISTRATION

4.1 General Guidelines for DF/HCC Institutions

Institutions will register eligible participants in the Clinical Trials Management System (CTMS) OnCore. Registrations must occur prior to the initiation of any protocol-specific therapy or intervention. Any participant not registered to the protocol before protocol-specific therapy or intervention begins will be considered ineligible and registration will be denied.

An investigator will confirm eligibility criteria and a member of the study team will complete the protocol-specific eligibility checklist.

CONFIDENTIAL

This document is confidential. Do not disclose or use except as authorized.

Following registration, participants may begin protocol-specific therapy and/or intervention. Issues that would cause treatment delays should be discussed with the Overall Principal Investigator (PI). If the subject does not receive protocol therapy following registration, the subject must be taken off-study in the CTMS (OnCore) with an appropriate date and reason entered.

4.2 Registration Process for DF/HCC Institutions

Applicable DF/HCC policy (REGIST-101) must be followed.

4.3 General Guidelines for Other Investigative Sites

N/A

4.4 Registration Process for Other Investigative Sites

N/A

5. TREATMENT

OVERALL TREATMENT PLAN

This is a Phase 1 study of CD25/Treg-depleted DLI plus Ipilimumab for eligible patients with relapsed myeloid malignancies after 8/8 HLA-matched donor bone marrow or peripheral blood stem cell transplantation. Donor CD25^{hi} cells will be depleted *ex-vivo* from peripheral blood mononuclear cells prior to infusion, and Ipilimumab will be administered after DLI. The study will follow a Phase 1 design in which matched-HCT recipients will receive escalating or de-escalating doses of CD25/Treg depleted donor lymphocytes and Ipilimumab. Patients will receive maintenance Ipilimumab per their assigned dose level.

5.1 Treatment Regimen

5.1.1 Patient preparation:

Prior to enrollment in the study, all patients will undergo a BM aspirate and biopsy (and/or biopsy of accessible extra-medullary disease sites, e.g. leukemia cutis) to confirm histologic or cytologic relapse. Patients may receive combination chemotherapy to control relapsed disease and/or re-induce remission if clinically indicated prior to DLI. Patients must have all cytotoxic or cytostatic agents (except hydroxyurea) discontinued at least 4 weeks prior to DLI (6 weeks for nitrosoureas or mitomycin C). Hydroxyurea may be instituted before or after the CD25/Treg-depleted donor lymphocyte infusion, if needed to temporarily control peripheral blood counts, after approval by the Study PI.

5.1.2 Donor Leukapheresis.

Prior stem cell donors will undergo apheresis to obtain donor lymphocytes. When possible, this

CONFIDENTIAL

This document is confidential. Do not disclose or use except as authorized.

will be performed via peripheral intravenous access. Donor evaluation, consents and apheresis may be performed at other centers (including international sites), and will require completion of appropriate consents and medical evaluations, per each donor center's standard operating procedures (SOPs). Apheresis for this study does not entail any added risk to the donor compared with unmodified DLI.

We anticipate that sufficient numbers of CD3+ donor lymphocytes will be collected from a single apheresis. After apheresis, an aliquot of the product will undergo analysis to determine the dose of CD3+ cells. Dosing will be determined by the CD3+ cells/kg as defined in **Table 2**. An aliquot will also be removed for microbiologic/sterility testing. If the collected product does not contain sufficient CD3+ cells (i.e. at least 1.5X the number of CD3+ cells/kg planned for infusion) the unmanipulated product will be administered off-study, dosed per the providers preference, and another patient will be recruited instead. The product, if adequate, will be processed per CMCF standard operating procedure and infused within the stated product expiration time.

5.1.3 Preparation and Infusion of CD25/Treg-depleted cells.

CD25/Treg depletion: All cell processing will be performed at the DFCI cGMP CMCF (Connell O'Reilly Cell Manipulation Core Facility). Upon receipt of sufficient donor leukapheresis product from the donor center, the product will be selectively depleted of CD25^{hi} Treg cells using the ClinIMACS® CD25 Reagent System according to manufacturer's instructions. A detailed protocol for the preparation and use of the ClinIMACS® CD25 reagent is provided to the clinical site in the ClinIMACS® User Manual. Samples of the donor leukocyte preparation will be removed prior to processing and after completion of the CD25^{hi} cell depletion. These samples will be used to determine cell viability, and enumerate the CD3+, CD4+, CD8+, CD14+, CD20+, CD25+, CD45+, CD56+, CD127+, and FOXP3+ cells (in combination as necessary, e.g. CD4+CD25^{hi}FOXP3+ cells) before and/or after processing. Gram stain, endotoxin and sterility testing will also be performed on the donor leukocyte preparation. The CD25^{hi} depleted product will be denoted as 'TC-T Reg (CD25^{hi}) reduced cells'. **Release criteria are indicated in Table**

1. Product will be infused even if the final CD3+ cell dose/kg is below target at the maximum number of cells available after requisite QC samples obtained.

If the total product collected contains <1.5-fold excess of CD3+ cells/kg per planned infusion dose, the product will NOT undergo CD25^{hi} depletion, and the unmanipulated product will be given to the patient, per institutional standards of care. The patient will not be assessable for the study objectives, and will be replaced by another patient.

If the total product collected contains ≥ 1.5 -fold excess of CD3+ cells/kg per planned infusion dose, then the product will be CD25^{hi} depleted with the ClinIMACS CD25 device according to manufacturer instructions. After depletion, the volume of processed product infused will be adjusted to the targeted CD3+ cell dose per the dose level schema, while maintaining $\leq 0.5\%$ CD4+CD25^{hi} cells. There will be no add back of the depleted fraction enriched for CD4+CD25^{hi} cells.

If the composition of the product after processing cannot meet both targets above, then the volume infused will be adjusted to best target their CD3+ dose per dose-level cohort. The patient will be unevaluable for DLT assessment.

CONFIDENTIAL

This document is confidential. Do not disclose or use except as authorized.

Table 1: Product Release Criteria

Test Performed	Test Method	Release Criteria
Viable CD3+ cell dose*	Flow Cytometry	Dose Level +2: 3×10^7 /kg Dose Level +1: 3×10^7 /kg Dose Level 0: 3×10^7 /kg Dose Level -1: 1×10^7 /kg
CD4+ CD25 ^{hi} cells	Flow cytometry	$\leq 0.5\%$ of viable lymphocytes
Viability	Trypan blue	$\geq 70\%$
Endotoxin	Charles River Endosafe® -PTS™ System	< 5.0 EU/Kg/hr
Gram stain	BWH Microbiology laboratory	No organisms

* Acceptable range: $0.8-1 \times 10^7$ viable CD3+ cells/kg for DL -1; $2.5-3 \times 10^7$ viable CD3+ cells/kg for DL 0, +1, +2

Donor Lymphocyte Infusion: The donor lymphocyte product will not be administered until it has passed the release criteria for infection control monitoring, as defined by the DFCI CMGTL and the FDA (**Table 1**). If release criteria (except CD3+ cell dose and CD4+CD25^{hi} cell fraction) are not met, the DLI product will NOT be infused, and the patient will be unevaluable for DLT assessment and will be replaced.

Once release criteria have been met, the DLI product will be infused into the recipient through a central or peripheral venous catheter, per the cell infusion SOP. The donor lymphocytes will be infused over 5-15 minutes. Acetaminophen 650mg PO and diphenhydramine 25mg IV or PO will be given as premedication prior to the infusion. Patients will be monitored for infusional reactions for 1 hour after the end of the infusion. Excess product, if any, will be cryopreserved per standard operating procedure for future use if necessary.

CD25/Treg-depleted DLI Dose Schema: Patients will receive a defined dose of CD25^{hi} Treg depleted DLI. 5 patients will be enrolled, initially at dose level 0, and subsequent cohorts will be dose adjusted per the CD3+ dose escalation/de-escalation schema detailed below.

Table 2: CD25/Treg-depleted DLI Dose Escalation/De-escalation Schema Per Cohort

Cohort	Viable CD3+ Dose* (#cells/kg)**
Dose Level +2	3×10^7
Dose Level +1	3×10^7
Dose Level 0	3×10^7
Dose Level -1	1×10^7

** Recipient's body weight in Kg

** Acceptable range: $0.8-1 \times 10^7$ viable CD3+ cells/kg for DL -1; $2.5-3 \times 10^7$ viable CD3+ cells/kg for DL 0, +1, and +2

CONFIDENTIAL

This document is confidential. Do not disclose or use except as authorized.

5.1.4 Ipilimumab administration.

Ipilimumab will be administered intravenously over 90 ± 10 minutes after the DLI product observation period is completed, and dosing will continue in 3-week intervals for 4 cycles, unless unacceptable toxicity or symptomatic disease progression occurs (see Appendices E-F for disease progression criteria). MTD will be assessed at day 43 by DLT criteria as defined in **Section 5.4**. At their day 92 evaluation, patients without evidence of progressive disease or unacceptable toxicity can receive maintenance Ipilimumab **per their assigned dose level** on a q 3 monthly basis starting from week 24, for 4 doses.

5.1.5 Dose-escalation/De-escalation schema: Four dose-level combinations of CD25/Treg-depleted DLI plus Ipilimumab will be evaluated to determine MTD.

Table 4: CD25/Treg-depleted DLI plus Ipilimumab Dose Escalation/De-escalation Schema Per Cohort

Cohort	Viable CD3+ Dose (#cells/kg*)	Ipilimumab Dose
Dose Level +2	3×10^7	10 mg/kg
Dose Level +1	3×10^7	3 mg/kg
Dose Level 0	3×10^7	1 mg/kg
Dose Level -1	1×10^7	1 mg/kg

** Recipient's body weight in Kg

** Acceptable range: $0.8-1 \times 10^7$ viable CD3+ cells/kg for DL -1; $2.5-3 \times 10^7$ viable CD3+ cells/kg for DL 0, +1, and +2

To ensure at least 3 patients will be evaluable within a group, a cohort of 5 eligible patients will enter at each dose level. If there are fewer than 3 evaluable patients in a cohort, additional patients will be added at that dose-level. Patients may be enrolled in the next cohort when 3 or more evaluable patients from the previous cohort have completed their day 43 assessment. Patients will be considered unevaluable for the determination of MTD if they require removal from the study due to alternative treatments for progressive disease (except hydroxyurea, with PI approval) or other reasons not related to an adverse event within 6 weeks after initial dosing. Additional patients may be enrolled at a specific dose cohort to substitute for patients within the cohort who are considered unevaluable for MTD. **There will be at least one-week interval between consecutive enrollments at the same dose level during phase 1A.**

Dose escalation or de-escalation is as follows: If ≤ 1 DLTs are observed within a cohort of up to 5 evaluable patients at dose level 0, then a dose escalation will take place. If ≤ 1 DLTs are observed at dose-level -1 or dose-level +2, this dose will be the MTD. If ≥ 2 DLTs are observed in a cohort of up to 5 evaluable patients, then the MTD is considered exceeded. If this is dose level 0, dose de-escalation will take place, and up to 5 patients will be enrolled at dose level -1. If ≥ 2 DLTs are observed at dose level +2, then dose level +1 will be the MTD. If ≥ 2 DLTs are observed at dose level -1, accrual will stop.

CONFIDENTIAL

This document is confidential. Do not disclose or use except as authorized.

5.1.7 Further Therapy for Patients with Progressive Disease: Treatment with hydroxyurea to temporarily control counts, with PI approval, will be acceptable on study. Patients who require additional therapy due to progressive disease will come off study to be treated at the discretion of the treating physician. Patients who receive off-study therapy (e.g. chemotherapy) will be followed for 1 year following DLI infusion for survival outcomes. Phase 1a patients who are removed from study without evidence of toxicity prior to their week 6 assessment (e.g. for progressive disease) will be considered unevaluable for MTD assessment, and will be replaced as necessary. **There will be at least one-week interval between consecutive enrollments at the same dose level during phase 1A.**

5.1.7 Phase 1b: In phase Ib, an additional 10 patients will be enrolled at the MTD to better define toxicity and describe preliminary efficacy at this dose level. No patients will be replaced in this phase.

5.2 Pre-Treatment Criteria

5.2.1 Cycle 1, Day 1

In order to start on therapy, subjects must meet all of the inclusion criteria outlined in Section 3.1, and must not have any of the exclusion criteria outlined in Section 3.2.

5.2.2 Other Cycles

To proceed with subsequent cycles, subjects must not have:

- grade 2 or higher acute GVHD (see **Appendix C** for GVHD grading) requiring systemic immunosuppression
- extensive (or severe) chronic GVHD requiring systemic immunosuppression
- ongoing non-hematologic toxicity of grade 2 or higher unrelated to underlying malignancy or GVHD

Subjects will be allowed to proceed to subsequent cycles if they have ongoing:

- immune-related adverse events not defined as GVHD (e.g. diarrhea, pruritus, endocrinopathy, and rash) that have responded to corticosteroids and improve to grade 1 or less

5.3 Agent Administration

Treatment will be administered on an outpatient basis. Reported adverse events and potential risks are described in **Section 6**. Dose modifications are not allowed in this study per **Section 6.1.3**. No investigational or commercial agents or therapies other than those described below may be administered with the intent to treat the patient's malignancy.

CONFIDENTIAL

This document is confidential. Do not disclose or use except as authorized.

5.3.1 Ipilimumab

Unit: Ipilimumab 5 mg/mL, in 10-mL or 40-mL vials

Route: Intravenous infusion

Appearance: Clear, colorless solution

Preparation, Handling, and Storage of Study Drug:

Please refer to **Section 8.1** for detailed information in this regard.

Drug administration and dosage schedule:

Induction Phase:

Ipilimumab is administered by IV infusion every 3 weeks for a total of four doses (Cycles 1-4). Infusions should be given over 90 +/- 10 minutes (not bolus or IV push).

Maintenance Phase:

Ipilimumab is administered by IV infusion every 12 weeks (3 months), beginning at Cycle 5, 24 weeks after the first dose of Ipilimumab, for up to 4 doses. Patients who show clinical benefit may be eligible to continue to receive Ipilimumab every 12 weeks beyond Cycle 8 with prior approval from the Study PI.

Dose delays are allowed as per the dosing criteria described later in this Section.

Dose Levels:

There will be three Ipilimumab dose levels in this study in separate cohorts:

Dose levels -1, 0: 1mg/kg

Dose level +1: 3 mg/kg

Dose level +2: 10 mg/kg

5.4 Definition of Dose-Limiting Toxicity (DLT)

Toxicities are to be assessed according to the NCI Common Toxicity Criteria for Adverse Events (CTCAE), Version 5.0 (**Appendix D**). DLT observation period is 42 days (6 weeks) after cell infusion plus Ipilimumab on day 1.

Definition of DLTs:

1. Development of solid organ/non-hematologic toxicity (exclusive of those attributable to

CONFIDENTIAL

This document is confidential. Do not disclose or use except as authorized.

GVHD or Immune-related AEs) of persistent CTCAE grade 3 (i.e. without improvement to Grade 1 or less within 3 weeks) or grade 4 or higher (any duration) within 6 weeks of cell infusion and considered possibly, probably, or definitely related to cells and/or Ipilimumab. Non-clinically significant metabolic adverse events (abnormalities in serum sodium, potassium, chloride, magnesium, calcium, phosphorous, blood urea nitrogen,

and glucose that last less than 48 hours that respond to appropriate medical therapy) will not be considered DLTs regardless of CTCAE grade. Infections are expected in the context of allotransplantation and relapse, and will not be considered DLTs.

2. Severe cytopenias (ANC < 500/ μ l and/or Plts < 20,000/ μ l) not related to the underlying disease or infections (e.g CMV) or other etiologies (e.g. emptying of relapsed bone marrow), occurring within 6 weeks after cell infusion, that persist despite 1 week of growth factor support (e.g., G-CSF or GM-CSF). Patients would be evaluated with a BM biopsy to assess for underlying disease vs. infection (e.g., CMV) vs. loss of relapsed host hematopoiesis. *If cytopenias are persistent, not explained by these or other transplant- or disease-associated causes, and possibly, probably or definitely related to cells and/or Ipilimumab, then the pancytopenia will be deemed a DLT.*
3. Acute GVHD: grade 3 or greater acute GVHD that does not improve to grade 2 or lower within 14 days of treatment.
4. Grade 3 or higher non-neurologic immune-related adverse events (e.g. diarrhea, pruritus, rash, endocrinopathies) that respond to corticosteroids and improve to grade 1 or less within 3 weeks will **NOT** count as DLTs. Biopsy of affected organs will be encouraged to help determine whether the immune-related condition is due to direct effects of Ipilimumab versus GVHD
5. CTCAE grade 3 and 4 infusion reactions related to the study DLI and/or the initial infusion of Ipilimumab.
6. Any grade 5 toxicity not due to underlying malignancy.

Management and dose modifications associated with the above adverse events are outlined in **Section 6** (Expected Toxicities and Dosing Delays).

Dose escalation will proceed within each cohort according to the scheme outlined in **Section 5.1.5**.

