6.1.4 Ipilimumab Discontinuation

Criteria that Require Permanent Discontinuation of Ipilimumab:

Subjects MUST discontinue study treatment for any of the following reasons that are not related to a related adverse event:

- Withdrawal of informed consent (subject's decision to withdraw for any reason)
- Pregnancy
- Termination of the study
- Loss of ability to freely provide consent through imprisonment or involuntary incarceration for treatment of either a psychiatric or physical (e.g., infectious disease) illness.

Subjects must permanently discontinue Ipilimumab if they experience any adverse event, laboratory abnormality or intercurrent illness that, in the judgment of the investigator, presents a substantial clinical risk to the subject with continued dosing.

The following neurological adverse events require permanent discontinuation of Ipilimumab and defines unacceptable neurotoxicity:

- Any neurologic motor toxicity \geq Grade 3 regardless of causality
- Any \geq Grade 3 treatment-related sensory neurologic toxicity

Ipilimumab need NOT be discontinued in the following situations:

- Potentially reversible inflammation ($<$ Grade 4), attributable to a local antitumor reaction and a potential therapeutic response
- Subjects with the following conditions where in the investigator's opinion continuing study drug administration is justified
- Ocular toxicity that has responded to topical therapy
- Endocrinopathies where clinical symptoms are controlled with appropriate hormone replacement therapy.

Note: Ipilimumab may not be restarted while the subject is being treated with systemic corticosteroids except for subjects on stable doses of hormone replacement therapy such as hydrocortisone for adrenal insufficiency.

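### Section 5.4 says which immune-related adverse events are not DLTs, but no item says which non-hematologic ones are

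*Combined protocol and SAP*

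**What the plan says.** Section 5.4 lists six numbered items under its definition of DLTs. Item 1 covers "Development of solid organ/non-hematologic toxicity (exclusive of those attributable to" and continues after the page break with "GVHD or Immune-related AEs) of persistent CTCAE grade 3 (i.e. without improvement to Grade 1 or less within 3 weeks", or grade 4 and above of any duration. The exclusion of irAEs carries no qualifier.

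Item 3 then gives acute GVHD a criterion of its own: "Acute GVHD: grade 3 or greater acute GVHD that does not improve to grade 2 or lower within 14 days of treatment". For irAEs the only matching text is item 4, which describes "Grade 3 or higher non-neurologic immune-related adverse events (e.g. diarrhea, pruritus, rash, endocrinopathies) that respond to corticosteroids and improve to grade 1 or less" and ends "within 3 weeks will NOT count as DLTs".

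Section 13.4 uses the count in two rules. Two or more DLTs at a dose level mean that the MTD is exceeded. In the Phase 1b expansion, at most 2 DLTs in 10 evaluable patients make the dose the recommended Phase II dose.

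**The concern.** Both GVHD and irAEs are taken out of item 1. Acute GVHD is put back by item 3. Nothing puts irAEs back, because item 4 only exempts some of them.

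The gap concerns a main expected toxicity of the drug being escalated. Section 6.1.2 warns of severe and fatal immune-mediated events with ipilimumab. Section 6.1.13 puts their usual onset at 3 to 10 weeks after the first dose, which overlaps the 6-week DLT window.

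Section 6.1.13 also expects irAEs and GVHD to be hard to tell apart clinically. The same severe gut or liver event can therefore be a DLT under item 3 if it is called acute GVHD, and meet no item if it is called an irAE. At stake are the primary endpoint (the MTD) and the Phase II dose recommendation.

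**Working it through.** **Step 1. Test a non-fatal, non-hematologic irAE against each item of Section 5.4.** Take one that falls outside item 4's exemption: unresolved at 3 weeks, steroid-refractory, or neurologic.

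| Item | Scope | Does the event count? |
|---|---|---|
| 1 | Non-hematologic toxicity, with GVHD and irAEs removed | No, excluded |
| 2 | Severe neutropenia or thrombocytopenia | No, though an immune-mediated cytopenia could: "possibly, probably or definitely related to cells and/or Ipilimumab, then the pancytopenia will be deemed a DLT" |
| 3 | Acute GVHD | No, unless the event is relabelled GVHD |
| 4 | Names irAEs that do not count | Silent on this event |
| 5 | Grade 3-4 infusion reactions | No, unless it is one |
| 6 | Grade 5 toxicity | No, as it is non-fatal |

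**Step 2. Look for a criterion elsewhere.** Sections 5.1.5, 11 and 13.4 use the DLT count but add no criterion. Section 6.1.4 says "The following neurological adverse events require permanent discontinuation of Ipilimumab and defines unacceptable neurotoxicity", but that governs stopping the drug and does not make the event a DLT.

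**Step 3. Try the inverse of item 4 as an implied rule.** It would count a non-neurologic irAE of grade 3 or higher that is unresolved at 3 weeks. It gives no grade threshold for neurologic irAEs. It also does not clearly classify a grade 3 irAE that resolves without corticosteroids. Two careful assessors could reach different counts.

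**Step 4. Reproduce the plan's own figures.** With 5 evaluable patients and DLT probability p, P(escalate) = (1-p)^5 + 5p(1-p)^4.
- p = 0.20: 0.3277 + 0.4096 = 0.737
- p = 0.30: 0.1681 + 0.3602 = 0.528

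Both agree with Table 8.

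For the expansion, P(≤2 of 10) = (1-p)^10 + 10p(1-p)^9 + 45p²(1-p)^8. This is 0.930 at p = 0.10 and 0.167 at p = 0.40. Section 13.4 prints 0.07 and 0.83 for these cases. Those are the probabilities of 3 or more DLTs (0.070 and 0.833). That is a separate labelling matter, noted here only so that the figures below can be compared.

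**Step 5. Illustrate the effect of the literal reading.** Let p be the true rate of unacceptable toxicity in the window, and s the share of those patients whose only qualifying event is an irAE that no item counts. The counted rate is q = p(1-s). The documents give neither p nor s, so both are assumptions.

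| True p | s | Counted q | P(escalate), 5 evaluable | P(≤2 of 10) |
|---|---|---|---|---|
| 30% | 0 | 30% | 0.528 | 0.383 |
| 30% | 25% | 22.5% | 0.685 | 0.602 |
| 30% | one third | 20% | 0.737 | 0.678 |
| 30% | 50% | 15% | 0.835 | 0.820 |
| 40% | 0 | 40% | 0.337 | 0.167 |
| 40% | 25% | 30% | 0.528 | 0.383 |
| 40% | 50% | 20% | 0.737 | 0.678 |

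For the one-third row, P(≤2 of 10) at q = 0.20 is 0.1074 + 0.2684 + 0.3020 = 0.678. At q = 0.30 it is 0.0282 + 0.1211 + 0.2335 = 0.383.

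**The case against.** The strongest reply is that item 4 stands in a list that defines DLTs, and that its qualifiers (non-neurologic, steroid-responsive, 3 weeks) would do no work if no irAE could ever count. Its 3-week, grade 1 test also mirrors the persistence test in item 1. The authors very likely meant irAEs that fail those conditions to count. This stands as a reading of intent, but it leaves the cases in step 3 undecided, and a primary endpoint should not rest on an implied clause.

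The trial's own history is a second reply. The DLTs that Section 13.4 identifies by type are GVHD, one of them fatal, and none falls in the gap. The December 2020 amendment closed dose level +2 after one DLT and returned to level 0 partly because of late SAEs, so the team did not act on the count alone. This weakens the practical consequence but does not supply the missing criterion.

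A reader might also infer three stronger points that the documents do not support:
- That items 1 and 4 contradict each other on grade 4. They do not: item 1 excludes irAEs, and item 4 expressly reaches grade 3 or higher, so the two classes simply have different thresholds.
- That Section 6.1.4 conflicts with Section 5.4. Stopping the drug and meeting a DLT are separate decisions.
- That the protocol calls immune and non-immune toxicity hard to separate. Section 6.1.13 says this of irAEs and GVHD. Section 6.1.9 asks for other causes to be ruled out before an event is labelled an irAE.

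**Conclusion.** Wrong as written. Section 5.4 excludes all irAEs from its non-hematologic criterion and never states which of them are DLTs. The finding is limited to non-fatal, non-hematologic irAEs that are not infusion reactions.

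If the text is applied literally, the counted DLT rate is biased downward, and both the MTD rule and the Phase 1b rule become easier to pass. The size cannot be derived from the documents. It is zero if no such events occurred, or if investigators counted them by inference. The change from 0.38 to 0.68 assumes a true rate of 30%, one third of it uncounted, and independent patients.

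A reader might go further and conclude that the DLT counts reported so far are too low. The documents do not show this: they do not list the recorded irAEs, and they do not say how any were classified.

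**What to change.** The sponsor should reconcile items 1 and 4 by stating affirmatively which irAEs are DLTs, neurologic ones included. The same paragraph should settle the case that item 4 leaves open, a severe irAE that resolves without corticosteroids. The thresholds are for the sponsor to set, and none is proposed here.

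The irAEs recorded in Phase 1a and Phase 1b should then be re-checked against the reconciled text, and any change in the DLT count reported. Dose level 0 matters most, because the expansion proceeds there.

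The cost is one paragraph of protocol text and a re-read of the CRFs. Section 6 already requires collection of all events of grade 3 or higher, so no new data are needed. The DLT count may become slightly less favourable.
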